#### 6.4.3.6 Intraocular pressure.

Tonometry is the objective measure of IOP, based primarily on the force required to flatten the cornea or the degree of corneal indentation produced by a fixed force. Goldman's tonometry is based on the Imbert-Fick principle. [38] The tonometry will be performed, after instillation of a drop of topical anesthetic (tetracaine 0.5%), with fluorescein and the use of the cobalt blue filter (after evaluation of the corneal surface staining). There will be 3 shots, which will be recorded in the clinical file and the average will be registered in the CRF.

#### 6.4.3.7 Posterior segment.

The evaluation of the posterior segment will be carried out under medication mydriasis (tropicamide 0.8% / phenylephrine 5%), in the slit lamp with an aerial loupe (at the choice of the PI). An integral assessment of the fundus (including optic disk, posterior pole and periphery) will be performed in search of abnormalities that alter the study result. The result of the assessment will be recorded in the clinical file. The CRF will record the assessment of the macula and optic nerve as normal, abnormal or abnormality that does not affect.

#### 6.4.3.8 Vital signs.

The vital signs to be evaluated (FC, FR and TAS) can be measured by an assistant duly indicated in the organization of the center and the delegation of responsibilities, the technique to be used for the FC and FR will be with the count of repetitions in one minute by Direct auscultation with stethoscope.

The SBP should be measured with 5 minutes of previous rest, in the left arm. The instrument can be manual or automatic according to the IP. It is necessary that all measurements are equal in circumstances. 3 measurements will be made, with a minimum interval of 5 minutes between them. The IP will record the average in the note and the CRF.

#### 6.4.3.9 Ocular symptomatology.

The subject will be questioned directly about the presence in general (since the last visit) of the following symptoms: burning, foreign body sensation and pruritus. Respond about the severity and frequency of symptoms such as:

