#### 6.4.3.2 Goblet cell density (Cytology per impression).

The density of goblet cells in the conjunctiva can be a reflection of the severity of alteration in the ocular surface. [39] It has been determined that the normal density is greater than 500 cel / mm2. [40] Impression cytology refers to the application of a cellulose acetate filter to the ocular surface to remove the superficial layers of the epithelium; these removed cells can be subjected to histological, immunohistological or molecular analysis. [41]

The cytology per impression of the conjunctiva will be done by the researcher using the device provided by the sponsor for this purpose, which may consist of a circular cell of approximately 10 mm in diameter, with a cellulose acetate filter millicell. After ocular surface anesthesia, with topical Sophia Laboratories, S.A. of C.V.

tetracaine, the researcher will ask the subject to expose the temporal surface of the eye to be evaluated and gently press the cell on the temporal conjunctiva (2 to 3 mm of the sclerocorneal limbus) for 5 seconds and remove the cell with a peeling technique (Illustration 1. Cytology per impression). Immediately fix with diethyl ether spray with one or two shots at 15 cm distance. The investigator will contact the Courier designated by the sponsor for the delivery of the samples to the histopathological analysis.

The data of the histopathological report to be recorded in the CRF are: density of goblet cells and degree of squamous metaplasia according to the Nelson scale. (See Table 6)

In the visits that are required to perform this procedure, it will be done prior to the use of ocular surface stains.

Illustration 1. Cytology per impression.

Grade	Detail description of the epithelial cells	Characteristics of goblet cells
0	Small and round cells; Large nuclei, 1: 2 ratio with nuclear cytoplasm	Abundant goblet cells (> 500 cells / mm2), globose and oval with an intense PAS-positive staining of the cytoplasm.
1	Slightly enlarged cells; smaller nuclei, 1: 3 ratio with nuclear cytoplasm	Marked decrease in the number of goblet cells (350 to 500 cells / mm2) but still maintain their globose and oval shape and intense staining
2	Enlarged and polygonal cells; small nuclei, ratio 1: 4 to 1: 5 with nuclear cytoplasm	Marked decrease in the number of goblet cells (100 to 350 cells / mm2), less intense PAS - positive with poorly defined cell borders

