#### Visit 1 / Day 3.

It can be done in a period  $\pm 1$  day in relation to day 3 of application.

- 1. Visual ability
- 2. Intraocular pressure.
- 3. Evaluation of ocular signs and symptoms
- 4. Integrity of ocular surface
  - a. Includes stains b. TRL
    - D. IKL
- 5. Vital signs
- 6. Evaluation of adverse events.

Sophia Laboratories, S.A. of C.V.

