# 6.5 6.5 Timeline and study diagram.

Procedures	Scrutiny	Basal Visit	Visit 1	Visit 2	Final Visit	Call Security
i loccuares		Day 0	Day 3 ± 1	Day 6 ± 1	Day 11 ± 1	Day 13 ± 1
CI Signature	Х					
Clinic history	Х					
Ophthalmological clinical history	Х					
Laboratory sample taking	Х				Х	
Laboratory tests review		Х				х
Pregnancy test	Х				Х	
Eligibility criteria	Х	Xa				
Assignment		Х				
Delivery of intervention		Х	Х	Х		
Return of intervention			Х	Х	Х	
Adherence evaluation			Х	Х	Х	
Adverse events			Х	Х	Х	Х
Intraocular pressure	Х	X1	Х	Х	Х	
Visual ability	Х	X1	Х	Х	Х	
TRL	Х	X1	Х	Х	Х	
Epithelial defects (TF and TVL)	Х	X1	Х	Х	Х	
Eye signs and symptoms	Х	X1	Х	Х	Х	
posterior segment	Х	X1			Х	
Vital signs	Х	X1	Х	Х	Х	
Ocular Comfort Index		Х			Х	
Goblet cell density (cytology by impression)		х			х	
Daily delivery of the subject		Х	Х	Х		
Return / Evaluation of the subject's Journal			Х	Х	х	
Delivery Quality Questionnaire		Х				
Return and Evaluation of the quality questionnaire					Х	
Continuity evaluation of the subject			Х	Х		

a The eligibility criteria will be completed with the revision of the laboratory exams. 1 These measurements may be taken from the result of the screening visit, if it does not exceed the previous 7 days. It is the prerogative of the PI to decide whether to repeat the measurements at the baseline visit.

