#### 6.5.1 Procedures to be performed per visit.

#### 6.5.1.1 Scrutiny visit.

- Signature of informed consent: refers to the signing of the written informed consent document. See 10.3 Consent (assent)
- General and ophthalmological clinical history: refers to the technical, clinical and legal document in which the patient's health conditions, medical acts and other procedures performed on the patient are recorded chronologically. It includes the anamnesis and comprehensive ophthalmological exploration that allows to discern the patient's eligibility. If the patient is taken from the established consultation of the study center, he / she will be able to use the existing clinical history, only having to perform an update.
- Taking laboratory samples: see 6.4.3.12 Laboratory tests.
- Pregnancy test: see 6.4.3.11 Pregnancy test.
- Eligibility criteria: refers to the review by the IP, where it states that the subject can be included in the study by meeting the inclusion criteria and not meeting the exclusion criteria. See 6.2 Eligibility criteria
- Intraocular pressure: see 6.4.3.6 Intraocular pressure
- Visual ability: see 6.4.3.1 Visual capacity
- TRL: see 6.4.3.10 Rupture time of the tear film
- Epithelial defects (TF and TVL): see 6.4.3.4.1 Stains
- Eve signs and symptoms: see 6.4.3.4 Eye surface integrity: and 6.4.3.9 Ocular symptomatology
- Subsequent segment; see 6.4.3.7 Subsequent segment
- Vital signs: see 6.4.3.8 Vital signs

6.5.1.2 Basal Visit .

- Review of laboratory tests: refers to the review and analysis by the IP of the results of the BH, QS and PFH. See 6.4.3.12 Laboratory tests.
- Eligibility criteria: with the laboratory results, the subject's profile will be finalized for inclusion or not.
- Assignment: It refers to determining the intervention that the patient will follow during the study. It will be done according to section 7. Methods. Assignment of the intervention. This assignment will be made at the baseline visit (day 0) and will go along with the indication to start the treatment period the next day (day 1).
- Delivery of intervention: Refers to the delivery of the product under investigation to the patient of the study, by the research center. It will be done according to sections 6.3.1 Managed treatments and 6.3.4.1 Delivery and reception.

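### At Visit 1 the graded burning, foreign body sensation and itching scores also cover the hours after the Day 0 cytology and before the first drop, so procedure symptoms can enter a tolerability score.

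*Combined protocol and SAP*

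**What the plan says.** Section 6.4.1.2 names burning, foreign body sensation, itching and the eye comfort index as the primary tolerability variables. Section 6.4.3.9 grades the three symptoms from 0 to 4 by direct questioning; the subject is "questioned directly about the presence in general (since the last visit) of the following symptoms". The same section also has a diary in which the subject marks the symptoms yes or no after each application. No section says which of the two records is the primary one.

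The visit content and timing are:

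- **Day 0.** The schedule in 6.5 marks "Goblet cell density (cytology by impression)" at the basal visit, without the footnote that lets other measurements be carried over from screening. Section 6.4.3.2 describes it as "application of a cellulose acetate filter to the ocular surface to remove the superficial layers of the epithelium", and the sampling is done "After ocular surface anesthesia, with topical" tetracaine.
- **Day 1.** Under 6.5.1.2 the assignment is given with the "indication to start the treatment period the next day (day 1)".
- **Visit 1.** Section 6.4.4 lists "Evaluation of ocular signs and symptoms" and allows one day either side of Day 3.

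Under 8.3.1 the product counts as safe and tolerable if no primary variable differs, clinically or statistically, from the comparators.

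**The concern.** The Visit 1 question looks back to Day 0, so its answer takes in what the subject felt after a filter was pressed on and peeled off the conjunctiva, before any study drop. Irritation from that step could plausibly be reported as burning, foreign body sensation or itching. The elimination criteria (6.2.3) separate intolerance of the test agents, tetracaine included, from intolerance of the study products. The symptom question cannot make that separation.

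The planned baseline score does not repair this. Signs and symptoms may be carried over from a screening visit up to 7 days earlier, before the cytology. If they are asked on Day 0, no order relative to the cytology is given. A rise from baseline to Visit 1 could then be procedural in part. Between arms, a component shared by all three makes a real product difference harder to see, and with 10 subjects per group a missed difference counts in the product's favour.

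**Working it through.** The plan states no figure on this point, so there is none to reproduce. The check has three steps.

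**1. Does the recall window contain pre-dose time?** The window runs from the Day 0 visit to Visit 1, and the first drop is on Day 1. With Visit 1 on Day 2, 3 or 4, Day 0 is one of 2, 3 or 4 calendar days (Day 0 up to the day before the visit), a share of 1/2, 1/3 or 1/4. These are upper limits, because only the part of Day 0 after the visit counts. No text excludes it. Cytology and its anaesthetic are certain on Day 0. Stains, tonometry and mydriasis fall on that day only if the investigator repeats them instead of using the screening results (6.5 footnote; 6.5.1.2).

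**2. Effect on a present/absent reading.** Table 5 classes the symptoms as nominal, and 8.3.1 analyses qualitative variables in 2×2 tables, so a two-way split is a natural reading; the cut is not stated. Let p be the share with the symptom from the product and q the share with it from the procedure, with independent causes:

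observed rate = 1 − (1 − p)(1 − q), so observed difference = (1 − q)(pA − pB).

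The documents give no q; 10% to 50% is assumed. For illustration take pA = 60% and pB = 8%. The 8% is the adverse event rate in 6.6.1. The 60% is the other percentage there, used here only as an assumed rate. Power is for two arms of 10 subjects, two-sided 5%, normal approximation.

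| q | observed rates | difference (points) | share of true | power |
|---|---|---|---|---|
| 0 | 60% v 8% | 52.0 | 1.00 | 72% |
| 10% | 64% v 17.2% | 46.8 | 0.90 | 58% |
| 30% | 72% v 35.6% | 36.4 | 0.70 | 36% |
| 50% | 80% v 54% | 26.0 | 0.50 | 23% |

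With assumed true rates of 40% v 8%, power falls from 38% at q = 0 to 16% at q = 30%.

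**3. Effect on a 0–4 score.** This was simulated with three arms of 10 and the Kruskal-Wallis test. Assumed probabilities for scores 0 to 4 are 0.40, 0.20, 0.20, 0.15, 0.05 in one arm and 0.80, 0.10, 0.06, 0.03, 0.01 in the other two. Procedure symptoms score 1, 2 or 3 with probabilities 0.50, 0.35, 0.15.

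- If the subject reports the worst symptom, the mean difference falls from 0.90 at q = 0 to 0.73 at q = 30% and 0.61 at q = 50%.
- If the scores add without a cap, the mean difference stays at 0.90, but at q = 30% the standard deviations rise from 1.26 and 0.81 to 1.52 and 1.17.
- Power falls either way: from about 50% at q = 0 to 28–29% at q = 30% (worst score, or sum capped at 4).

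The loss of power thus appears under both reporting models. The shrinkage of the difference itself depends on how subjects combine the two sources.

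**The case against.** The strongest reply is that randomised arms with identical procedures already control for procedure symptoms. They cannot create a false difference, and the decision rule compares arms, so neither a rise within a group nor the lack of an untreated arm decides anything. That stands as far as it goes: the expected cost is lost sensitivity, not a bias towards finding a difference. Under a rule that rewards finding none, lost sensitivity still matters.

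The second reply is that other records escape the problem. The diary is tied to each drop. The comfort index asks how often and how intensely the eyes felt gritty, stung or itched in the last week. At a Final Visit on Day 10 to 12 that week starts on about Day 3 to 5. This also stands. A reader might infer that the questioned scores are the only graded symptom data; the comfort index shows otherwise. The diary, however, has no grades.

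Third, section 5.1 calls impression cytology minimally invasive, 6.4.3.2 describes gentle pressure for 5 seconds, and the frequency grade limits what a brief symptom can add over several days. So q may be small. Nothing in the documents settles it.

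A reader might also extend the point to Visit 2 and the Final Visit, whose windows follow stains, anaesthetic and tonometry at the preceding visit. Those windows lie wholly within dosing and contain no earlier cytology. Cutting the visit-day hours from them would remove on-treatment time from a safety score.

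**Conclusion.** The point holds for Visit 1. The graded score includes a post-cytology, pre-dose period in every arm, and the baseline score may predate that cytology. The result is added noise and, for present/absent or worst-severity reporting, a diluted difference between arms.

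The size cannot be stated from the documents. The factor (1 − q) assumes independent causes and a present/absent reading, and every value of q and every product rate used above is an assumption. How far it affects the conclusion also depends on which symptom record is primary and at which visit, and neither is specified.

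Two stronger readings are not supported. One is that real product differences will shrink by a known amount: with additive scores the mean difference is unchanged, and no procedure rate is given. The other is that the whole tolerability assessment is compromised: the diary, the comfort index at the Final Visit and the later questioned scores do not reach back to Day 0.

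**What to change.** In 6.4.3.9, word the Visit 1 question as 'since your first drop on Day 1'. Keep the present recall period for Visit 2 and the Final Visit.

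Optionally, have the subject record the same three symptoms on the same 0–4 scale just before the first drop, and use that entry as the pre-dose reference for the Visit 1 score. A yes/no entry would not serve, because the score it has to be compared with is graded.

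The cost is one visit-specific CRF wording and at most one diary entry; no visit, procedure or sample size changes. One limit remains: cytology symptoms that persist into Day 1 would still be counted at Visit 1 unless the pre-dose entry is used.

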#### Severity: Absent (0), very mild (1), mild (2), moderate (3) and severe (4)

Frequency: At all times (4), almost at all times (3), 50% of the time (2), almost at no time (1), at any time (0).

The number corresponding to each symptom will be registered in the CRF.

#### Symptomatology postinstilación:

The subject will be requested, that in the subject's daily instrument, after registering the application of the product under investigation, mark YES or NO according to the presence of the following symptoms: burning, sensation of a foreign body, red eye and pruritus.

#### 6.4.3.10 Breaking time of the tear film.

One of the first aspects of the tear film that changes when there is an alteration to the ocular surface, is its stability. In general, if the corneal or conjunctival surface is damaged, it is unlikely that a stable tear film can be maintained.

The most common method to evaluate the stability of the tear film is the evaluation of TRL with fluorescein. Once the fluorescein is instilled, with the cobalt blue filter the patient is asked not to blink. The precorneal colored fluorescein layer will change to less fluorescent or non-fluorescent

regions. The time that elapses from the last blink until the appearance of these regions is the TRL. It will be reported in seconds, in the clinical file and in the CRF.

#### 6.4.3.11 Pregnancy test.

It refers to the performance of a rapid pregnancy test in all women of childbearing age who wish to enter the study. By fertile age we understand women who have not had their menopause, defined as 12 months since the last menstrual period in women over 40 years of age; or those who underwent bilateral hysterectomy or oophorectomy. Women of childbearing age with contraceptive methods including bilateral tubal obstruction should be tested for pregnancy. This test will be carried out by the IP or the designated team person according to the instructions of the device delivered by the sponsor. When applicable, the completion, result and date must be registered in the CRF. If you do not apply, you must write down the reason.

#### 6.4.3.12 Lab tests.

The PI will deliver to the subject the order of the studies of BH, QS and PFH, to be carried out in the clinical laboratory designated by the sponsor. The clinical laboratory will deliver to the IP the results for its assessment and registration. The normal parameters to be considered will be the ranges established by the laboratory, Nevertheless the clinical criterion of the PI will prevail in the decision of normality or abnormality of the results.

#### 6.4.4 Measurement time.

The measurements of the variables of primary and secondary outcome will be made and evaluated for each visit, according to the following:

#### Basal Visit / Day 0.

Some of these measurements will be taken at the screening visit to complete the eligibility criteria (see Schedule and study diagram), at the discretion of the PI, they may be taken to complete the data of the baseline visit.

- 1. Visual ability
- 2. Density of goblet cells (Cytology per impression)
- 3. Intraocular pressure.
- 4. Eye comfort index
- 5. Evaluation of ocular signs and symptoms
- 6. Integrity of ocular surface
  - a. Includes stains
  - b. TRL
- 7. Subsequent segment evaluation.
- 8. Vital signs
- 9. Evaluation of results of laboratory tests.

#### Visit 1 / Day 3.

It can be done in a period  $\pm 1$  day in relation to day 3 of application.

- 1. Visual ability
- 2. Intraocular pressure.
- 3. Evaluation of ocular signs and symptoms
- 4. Integrity of ocular surface
  - a. Includes stains b. TRL
    - D. IKL
- 5. Vital signs
- 6. Evaluation of adverse events.

Sophia Laboratories, S.A. of C.V.

# Visit 2 / Day 6.

It can be done in a period  $\pm 1$  day in relation to the 6th day of application.

- 1. Visual ability
- 2. Intraocular pressure.
- 3. Evaluation of ocular signs and symptoms
- 4. Integrity of ocular surface
  - a. Includes stains b. TRL
- 5. Vital signs
- 6. Evaluation of adverse events.

# Final Visit / Day 11.

It can be done in a period  $\pm 1$  day in relation to the 11th day of the start of application.

- 1. Visual ability
- 2. Density of goblet cells (Cytology per impression)
- 3. Intraocular pressure.
- 4. Eye comfort index
- 5. Evaluation of ocular signs and symptoms
- 6. Integrity of ocular surfacea. Includes stainsb. TRL
- 7. Subsequent segment evaluation.
- 8. Vital signs
- 9. Evaluation of adverse events.

#### Security call / Day 13.

It can be done in a period  $\pm 1$  day in relation to the 13th day of the start of application.

- 1. Ask about the presence of an adverse event.
- 2. Evaluation of results of laboratory tests

# 6.5 6.5 Timeline and study diagram.

Procedures	Scrutiny	Basal Visit	Visit 1	Visit 2	Final Visit	Call Security
i loccuares		Day 0	Day 3 ± 1	Day 6 ± 1	Day 11 ± 1	Day 13 ± 1
CI Signature	Х					
Clinic history	Х					
Ophthalmological clinical history	Х					
Laboratory sample taking	Х				Х	
Laboratory tests review		Х				х
Pregnancy test	Х				Х	
Eligibility criteria	Х	Xa				
Assignment		Х				
Delivery of intervention		Х	Х	Х		
Return of intervention			Х	Х	Х	
Adherence evaluation			Х	Х	Х	
Adverse events			Х	Х	Х	Х
Intraocular pressure	Х	X1	Х	Х	Х	
Visual ability	Х	X1	Х	Х	Х	
TRL	Х	X1	Х	Х	Х	
Epithelial defects (TF and TVL)	Х	X1	Х	Х	Х	
Eye signs and symptoms	Х	X1	Х	Х	Х	
posterior segment	Х	X1			Х	
Vital signs	Х	X1	Х	Х	Х	
Ocular Comfort Index		Х			Х	
Goblet cell density (cytology by impression)		х			х	
Daily delivery of the subject		Х	Х	Х		
Return / Evaluation of the subject's Journal			Х	Х	х	
Delivery Quality Questionnaire		Х				
Return and Evaluation of the quality questionnaire					Х	
Continuity evaluation of the subject			Х	Х		

a The eligibility criteria will be completed with the revision of the laboratory exams. 1 These measurements may be taken from the result of the screening visit, if it does not exceed the previous 7 days. It is the prerogative of the PI to decide whether to repeat the measurements at the baseline visit.

#### 6.5.1 Procedures to be performed per visit.

#### 6.5.1.1 Scrutiny visit.

- Signature of informed consent: refers to the signing of the written informed consent document. See 10.3 Consent (assent)
- General and ophthalmological clinical history: refers to the technical, clinical and legal document in which the patient's health conditions, medical acts and other procedures performed on the patient are recorded chronologically. It includes the anamnesis and comprehensive ophthalmological exploration that allows to discern the patient's eligibility. If the patient is taken from the established consultation of the study center, he / she will be able to use the existing clinical history, only having to perform an update.
- Taking laboratory samples: see 6.4.3.12 Laboratory tests.
- Pregnancy test: see 6.4.3.11 Pregnancy test.
- Eligibility criteria: refers to the review by the IP, where it states that the subject can be included in the study by meeting the inclusion criteria and not meeting the exclusion criteria. See 6.2 Eligibility criteria
- Intraocular pressure: see 6.4.3.6 Intraocular pressure
- Visual ability: see 6.4.3.1 Visual capacity
- TRL: see 6.4.3.10 Rupture time of the tear film
- Epithelial defects (TF and TVL): see 6.4.3.4.1 Stains
- Eve signs and symptoms: see 6.4.3.4 Eye surface integrity: and 6.4.3.9 Ocular symptomatology
- Subsequent segment; see 6.4.3.7 Subsequent segment
- Vital signs: see 6.4.3.8 Vital signs

6.5.1.2 Basal Visit .

- Review of laboratory tests: refers to the review and analysis by the IP of the results of the BH, QS and PFH. See 6.4.3.12 Laboratory tests.
- Eligibility criteria: with the laboratory results, the subject's profile will be finalized for inclusion or not.
- Assignment: It refers to determining the intervention that the patient will follow during the study. It will be done according to section 7. Methods. Assignment of the intervention. This assignment will be made at the baseline visit (day 0) and will go along with the indication to start the treatment period the next day (day 1).
- Delivery of intervention: Refers to the delivery of the product under investigation to the patient of the study, by the research center. It will be done according to sections 6.3.1 Managed treatments and 6.3.4.1 Delivery and reception.
- Evaluation of variables: The data of the evaluation of the variables listed below can be taken from the scrutiny visit, as long as it does not exceed 7 days prior to this visit. It is the prerogative of the IP to decide whether to use the information from the screening visit or to repeat the evaluations in this visit.
  - Intraocular pressure
  - o Visual capacity
  - TRL
  - Epithelial defects
     Eye signs and symptoms

- Subsequent segment
- vital signs
- Eye comfort index: see 6.4.3.3 Eye comfort index
- Density of goblet cells (cytology per impression): see 6.4.3.2 Density of goblet cells (cytology per impression)
- Delivery of the subject's diary: It refers to the delivery by the IP to the subject, the subject's daily instrument.
- Delivery of quality questionnaire: It refers to the delivery by the IP to the subject, the quality questionnaire instrument.

